8.7 Medical Resource Utilization and Health Economics

Patient-reported questionnaires will be collected via a paper source document according to the Schedule of Activities

EORTC QLQ-C30

Health-related quality of life will be assessed with the European Organization for Research and Treatment of Cancer Quality of Life Questionnaire Core 30 Version 3.0 (EORTC QLQ-C30; Aaronson et al. 1993).

The EORTC QLQ-C30 self-reported general cancer instrument consists of 30 items covered by 1 of 3 dimensions:

- global health status/quality of life (2 items)
- functional scales (15 total items addressing either physical, role, emotional, cognitive, or social functioning)
- symptom scales (13 total items addressing either fatigue, nausea/vomiting, pain, dyspnea, insomnia, appetite loss, constipation, diarrhea, or financial impact)

Bowel Diary (for MTC patients only)

Bowel Diary adapted and modified from patient-reported questionnaire (STIDAT) by Michelle Lui et al., Development and validation of a patient-reported questionnaire assessing systemic therapy induced diarrhea in oncology patients, *HEALTH AND QUALITY OF LIFE OUTCOMES* 15:249 (2017). Copyright © 2017 Michelle Lui, Daniela Gallo-Hershberg and Carlo DeAngelis (Lui, Gallo-Hershberg et al. 2017). STIDAT distributed as-is and as-available, with no warranties, under the Creative Commons Attribution 4.0 International License (<https://creativecommons.org/licenses/by/4.0/legalcode>).

9 Statistical Considerations

A full Statistical Analysis Plan (SAP) will provide specific details on the analytical methods and data displays.

9.1 Study Endpoints

9.1.1 Primary Endpoint

- ORR using RECIST v1.1 as assessed by independent review committee (IRC).

9.1.2 Secondary Endpoints

- Parameters of anti-tumor activity/clinical benefit, including: ORR (by Investigator), DOR (by IRC and Investigator), CNS ORR (by IRC), CNS DOR (by IRC), time to any and best response (by IRC and Investigator), CBR (by IRC and Investigator), PFS (by IRC and Investigator), and OS
- Frequency, severity, and relatedness of TEAEs and SAEs, changes in hematology and blood chemistry values, and assessments of physical examinations, vital signs, and ECGs
- Plasma concentrations of selpercatinib and PK parameters, including, but not limited to, AUC_{0-24} , C_{max} , and T_{max}

9.1.3 Exploratory Endpoints

- Differences in efficacy and safety based on selpercatinib PK parameters
- Changes in CEA and calcitonin (patients with MTC), thyroglobulin (non-MTC thyroid cancer patients), and ACTH and cortisol (patients with Cushing's disease related to their cancer) with selpercatinib treatment
- Changes from baseline in disease-related symptoms and HRQoL, as measured by EORTC QLQ-C30, and patient bowel diaries (MTC patients only)
- Time from PD₁ to PD₂ for patients who continue to receive study treatment beyond disease progression

9.2 Analysis Populations

Enrolled population: will include all enrolled patients.

Treated population will include all enrolled patients who received at least one dose of selpercatinib. This population will be used for safety analysis and efficacy analysis other than primary efficacy analysis.

Primary efficacy analysis population: will include all treated patients enrolled in Cohort 1 and 2 who have confirmed RET fusion positive solid tumor or RET mutant MTC by central lab, respectively. The primary efficacy analysis will be conducted on this population.

Pharmacokinetic population will include all treated patients with baseline and at least one postbaseline evaluable PK sample.

9.3 Determination of Sample Size

For Cohort 1-2, at least 20 patients will be targeted for enrollment in each cohort. The main objective is to provide for a preliminary assessment of the antitumor activity of selpercatinib in Chinese patients with RET alterations. [Table 9-1](#) presents the lower bounds of 2-sided exact 95% confidence intervals based on different choice of sample size and observed ORR. If the observed ORR is high (i.e., exceeds 45%) within a cohort of 20 patients, then the corresponding lower limit of a 2-sided exact 95% confidence interval will exclude true response rates that are considered marginal or uninteresting.

Up to 25 patients will be enrolled into Cohort 3 based on clinical considerations.

In addition, with an overall sample size of 75, the probability of observing one or more instances of a specific AE with a true incidence rate of 2% and 5% is approximately 80% and 98%, respectively.

Table 9-1 Lower bounds of 2-sided exact 95% confidence intervals based on different sample size and observed ORR

| n \ ORR | 0.4 | 0.45 | 0.5 | 0.55 | 0.6 | 0.65 |
|---------|------|------|------|------|------|------|
| 10 | 0.12 | 0.15 | 0.19 | 0.22 | 0.26 | 0.3 |
| 20 | 0.19 | 0.23 | 0.27 | 0.32 | 0.36 | 0.41 |
| 25 | 0.21 | 0.25 | 0.30 | 0.34 | 0.39 | 0.44 |
| 30 | 0.23 | 0.27 | 0.31 | 0.36 | 0.41 | 0.46 |
| 40 | 0.25 | 0.29 | 0.34 | 0.38 | 0.43 | 0.48 |
| 50 | 0.26 | 0.31 | 0.36 | 0.40 | 0.45 | 0.50 |
| 60 | 0.28 | 0.32 | 0.37 | 0.42 | 0.47 | 0.52 |

9.4 Statistical Methods

9.4.1 Demographics and Baseline Characteristics

Descriptive summaries of demographic and baseline characteristics for all enrolled patients will be tabulated. Patients will be tabulated by cohort and overall.

9.4.2 Safety Analyses

Safety will be assessed by clinical review of all relevant parameters including AEs, SAEs, laboratory values, vital signs, ECG results, concomitant medications, and thyroid function. Unless specified otherwise, the safety analyses will be conducted for the safety population defined in Section 8.2 from all cohorts. Tabulations will be provided by cohort and overall.

Summary tables and listings will be provided for all reported TEAEs, defined as AEs that start on or after the first administration of study drug. The reported AE term will be assigned standardized coding using MedDRA; the MedDRA version shall be specified in study documents.

TEAEs will be summarized based on the number and percentage of patients experiencing the event by MedDRA System Organ Class (SOC) and preferred term (PT). The causal relationship between the occurrence of an AE and study drug will be judged by the Investigator based on the conventions described in Section 8.2. In the event a patient experiences repeat episodes of the same AE, then the event with the highest severity grade and strongest causal relationship to study drug will be used for purposes of incidence tabulations.

Tabular summaries will be provided for:

- All TEAEs.
- TEAEs by relationship (yes, no) to underlying disease, other medical conditions or concomitant medications, and maximum severity grade.
- TEAEs with action of study drug delayed/interrupted or treatment reduced.
- TEAEs with action of study drug discontinued.
- All SAEs.
- SAEs by relationship (yes, no) to underlying disease, other medical conditions, or concomitant medications.

All deaths including on-study death that occur within 28 days of treatment discontinuation will be reported in a patient listing, which will include the primary cause of death and the number of days

between the date of the last dose of study drug and death. A summary of the anticancer therapies received after discontinuation of study drug will be provided.

Hematology and serum chemistries will be summarized in a descriptive manner by calculating the mean, standard deviation, median, and range.

9.4.3 Efficacy Analyses

The efficacy analyses will be conducted on the efficacy population unless otherwise specified.

Tumor response will be assessed using RECIST 1.1 (Table 11-8). The objective response rate (ORR) is defined as the number of patients who achieve a best overall response of complete response (CR) or partial response (PR) that are confirmed divided by the total number of efficacy analysis population. ORR, accompanied by 2-sided 95% exact binomial CIs, will be summarized. The analysis of ORR will be conducted both by the responses determined by IRC and investigator.

Waterfall plots will be used to depict graphically the maximum decrease from baseline in the sum diameters of target lesions.

DOR will be calculated for patients who achieve CR or PR. For such patients, DOR is defined as the number of months from the start date of CR or PR (whichever response status is observed first) and subsequently confirmed, to the first date that PD is objectively documented. If a patient dies, irrespective of cause, without documentation of PD beforehand, then the patient's date of death will be used to denote the response end date.

PFS will be derived for each patient as the number of months from the date of the first dose of study drug to the earlier of documented PD or death due to any cause. Patients who are alive and without documented PD as of a data analysis cutoff date will be right-censored.

OS will be derived for each patient as the number of months from the date of the first dose of study drug to the date of death, irrespective of cause. Patients who are alive or lost to follow-up as of a data analysis cutoff date will be right-censored. The censoring date will be determined from the last date the patient was known to be alive or data analysis cutoff date, whichever occurs first.

The detailed censoring rule for lifetime data such as DOR, PFS and OS will be specified in SAP. DOR, PFS, and OS will be summarized descriptively using the Kaplan-Meier method with 95%

CI. Median follow-up for each endpoint will be estimated according to the Kaplan-Meier estimate of potential follow-up ([Schemper and Smith 1996](#)).

Analyses of other secondary and exploratory endpoints will be provided in the SAP.

9.4.4 Pharmacokinetic Analyses

Plasma concentrations of selpercatinib will be determined with a validated bioanalytical assay. The following PK parameters will be calculated from plasma concentrations determined on C1D8: C_{max} , T_{max} , area under the concentration versus time curve from time 0 to t (AUC_{0-t}), $AUC_{0-\infty}$, apparent oral clearance (CL/F), apparent volume of distribution (V_z/F), and $T_{1/2}$.

Summary statistics will be generated by cohorts as appropriate.

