ORR will be estimated based on the observed proportion of patients whose best overall response is confirmed CR or PR as determined by IRC and by the treating Investigator. The estimates of the ORR will be accompanied by a 2-sided 95% exact binomial confidence interval (CI). Waterfall plots will be used to depict graphically the maximum decrease from baseline in the sum of diameters of target lesions. The duration of response, PFS, and OS will be summarized descriptively for each cohort using the Kaplan-Meier method.

Pharmacokinetic Analyses:

Plasma concentrations of seliperatinib will be determined with a validated bioanalytical assay. The following PK parameters will be calculated from plasma concentrations determined on Cycle 1 Day 1 and Day 8: C_{max} , T_{max} , area under the concentration versus time curve from time 0 to t (AUC_{0-t}), area under the concentration time curve from time 0 to infinity ($AUC_{0-\infty}$), apparent oral clearance (CL/F), apparent volume of distribution (Vz/F), and terminal elimination half-life ($T_{1/2}$). Summary statistics will be generated by cohort as appropriate.

Table of Contents

| | |
|---|----|
| Protocol Amendment Summary of Changes Table | 2 |
| Synopsis..... | 3 |
| Table of Contents..... | 10 |
| List of Tables | 13 |
| List of Figures..... | 14 |
| List of Appendices | 15 |
| List of Abbreviations and Definition of Terms | 16 |
| 1 Introduction | 21 |
| 1.1 Tumors with RET Abnormalities and Current Treatment Options | 21 |
| 1.2 Study Rationale..... | 23 |
| 1.3 Selpercatinib Pre-clinical Data Summary | 23 |
| 1.4 Determination Starting Dose | 24 |
| 1.5 Clinical Experience | 24 |
| 1.6 Benefit and Risk Assessment..... | 26 |
| 1.6.1 Known and Anticipated Risks | 26 |
| 1.6.2 Potential Drug Interactions..... | 27 |
| 2 Study Objectives..... | 30 |
| 2.1 Primary Objective | 30 |
| 2.2 Secondary Objectives..... | 30 |
| 2.3 Exploratory Objectives..... | 30 |
| 3 Investigational Plan..... | 32 |
| 3.1 Study Design..... | 32 |
| 3.2 Length of Study and End of Study..... | 32 |
| 3.2.1 Length of Study | 32 |
| 3.2.2 End of Study | 33 |
| 3.3 General Treatment Procedures..... | 33 |
| 3.4 Investigational Plan..... | 34 |
| 3.5 Definition of RET Alterations..... | 36 |
| 3.6 Number of Patients..... | 36 |
| 3.7 Investigational Sites | 36 |
| 4 Selection of Study Population | 37 |
| 4.1 Inclusion Criteria..... | 37 |
| 4.2 Exclusion Criteria | 40 |
| 5 Enrollment Procedures | 42 |

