6.3.2 Allowed Concomitant Medications

Standard supportive medications may be used in accordance with institutional guidelines and Investigator discretion. These may include hematopoietic growth factors to treat neutropenia, anemia or thrombocytopenia (in countries where hematopoietic growth factors are approved for use) in accordance with American Society for Clinical Oncology guidelines (but not for prophylaxis in C1); RBC and platelet transfusions, anti-emetic, analgesic and antidiarrheal medications; electrolyte repletion (e.g., calcium and magnesium) to correct low electrolyte levels; conditional use of steroids treatment as indicated in Section 6.3.3; thyroid replacement therapy for

hypothyroidism; and bisphosphonates, denosumab; and other medications for the treatment of osteoporosis, prevention of skeletal-related events from bone metastases, and /or hypoparathyroidism. Continuation of standard of care medications, including adjuvant hormonal therapy for patients with prostate cancer (e.g., gonadotropin-releasing hormone [GnRH] or luteinizing hormone-releasing hormone [LHRH] agonists) and breast cancer (e.g., GnRH/LHRH agonists, aromatase inhibitors, selective estrogen receptor modulators [SERMs] or degraders [SERDs]), that the patient has been on for the previous 28 days, are allowed, provided they are not on the list of prohibited concomitant medications (refer to Section 6.3.3 and Appendix D).

Local treatment while receiving selpercatinib (e.g., palliative radiation therapy or surgery for bone metastases) is permitted with Sponsor approval; however, the Sponsor recommends holding selpercatinib for approximately 5 half-lives (approximately 2 to 3 days) before and after radiation therapy or surgery. Any concern for disease flare due to a prolonged period off from selpercatinib should be discussed with the Sponsor, who may permit holding selpercatinib for a shorter period of time.

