The procedures listed below will be performed at the indicated intervals. Observations, routine laboratory tests, and HRQoL assessments will be performed prior to selpercatinib dosing on that day unless otherwise indicated. Routine clinic visits and C1D1 evaluations performed within - 2 days of the nominal visit day will not be considered protocol deviations, with the exception of ECGs, PKs, and vital signs, which must be performed relative to the dose of selpercatinib on that day as indicated below.

Day 1

- Symptom-directed physical examination, weight, and ECOG.
- Vital signs: pre-dose (up to 4 hours pre-dose, as close to dosing as possible is preferred) and 2 hours post-dose (± 30 minutes). Vital signs should be performed prior to collection of PK blood sample drawn at that time point.
- Resting 12-lead ECG: pre-dose (up to 4 hours pre-dose).
- Serum or urine pregnancy test for women of childbearing potential (surgically sterilized females or those who have not experienced menses for at least 2 years are not required to be tested i.e., post-menopausal women who have not had menses within the last 12 months, but have had menses within the last 24 months will be required to have a serum pregnancy test performed).
- Hematology (as described in [Appendix H](#)).
- Serum chemistries (as described in [Appendix H](#)).
- Blood sample of intensive PK (2 mL whole blood) for a total 12 subjects: pre-dose, and post-dose at 1 hour (± 15 minutes), 2 hours (± 15 minutes), and 4 hours (± 15 minutes), 8 hours (± 30 minutes) and 12 hours (± 30 minutes). Exact clock time (24h format) of sample collection and of dose administration should be recorded.
- Blood sample of PopPK (2 mL whole blood) for all enrolled subjects: each cycle D1 predose.
- Coagulation (as described in [Section 7.1](#)).
- Calcitonin, CEA: for patients with MTC only. For each patient, all tests for calcitonin and CEA should be performed in the same laboratory to minimize intra-patient, lab-to-lab variability in their measurement.
- Thyroglobulin: for patients with non-MTC thyroid cancer only (unless not measurable due to presence of anti-thyroglobulin antibodies). For each patient, all tests for thyroglobulin should be performed in the same laboratory to minimize intra-patient, lab-to-lab variability in their measurement.
- Blood cortisol, ACTH, 24-hour urine for free cortisol: optional for patients with Cushing's disease related to their cancer. If done, urine collection should begin pre-dose.

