- Dispense selpercatinib.
- Selpercatinib administration.
- Outpatient diaries for recording daily selpercatinib dosing, H2 blockers and antacids.
- AEs.
- Concomitant medications.
- Patient-reported outcomes to be completed pre-dose:
 - For MTC patients with diarrhea present at baseline: bowel diary.
 - European Organization for Research and Treatment of Cancer Quality of Life Questionnaire-Core 30 (EORTC QLQ-C30).

Day 8

- Symptom-directed physical examination, weight, and ECOG.
- Vital signs: pre-dose (up to 4 hours pre-dose, as close to dosing as possible is preferred) and 2 hours post-dose (± 30 minutes). Vital signs should be performed prior to collection of PK blood sample drawn at that time point.
- Resting 12-lead ECG: perform a single ECG at 2 hours (± 10 minutes) post-selpercatinib dosing. On C1D8 PK collection, an extra ECG should be timed prior to the PK sample being drawn. If any ECG demonstrates QTcF 481-500 msec, perform an additional ECG at the same day, specific time judged by investigator. If any ECG demonstrates QTcF > 500 msec, repeat the ECG twice (triplicate in total) at the same day, specific time judged by investigator, and manually review to confirm accuracy.
- Hematology (as described in [Appendix H](#)).
- Serum chemistries (as described in [Appendix H](#)).
- Blood sample of intensive PK (2 mL whole blood) for a total 12 subjects: pre-dose, and post-dose at 1, 2 and 4 hours (± 15 minutes), and 8 hours (± 30 minutes). Exact clock time (24h format) of sample collection and of dose administration should be recorded.
- Outpatient diaries for recording daily selpercatinib dosing, H2 blockers, and antacids.
- AEs.
- Concomitant medications.
- For MTC patients with diarrhea present at baseline: bowel diary.

Day 15

- Symptom-directed physical examination, weight, and ECOG.
- Vital signs: pre-dose (up to 4 hours pre-dose, as close to dosing as possible is preferred).
- Hematology (as described in [Appendix H](#)).
- Serum chemistries (as described in [Appendix H](#)).
- Thyroid panel, including TSH, FT₃, and FT₄.
- Urinalysis.
- Calcitonin, CEA: for patients with MTC only. For each patient, all tests for calcitonin and CEA should be performed in the same laboratory to minimize intra-patient, lab-to-lab variability in their measurement.

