7.7.3 Pharmacokinetics

Plasma samples will be obtained for patients as outlined in SoA. Additional PK assessments may be conducted in patients when considered necessary by the Investigator to understand exposure in relationship to possible safety or efficacy findings or if there is a change to the formulation of selpercatinib administered. Samples will be collected and handled as outlined in the Laboratory Manual, and concentrations of selpercatinib will be determined with a validated bioanalytical method. These data will be used to determine parameters such as AUC_{0-t} and plasma terminal elimination half-life ($T_{1/2}$). The 0-8-hour duration of sample collection will be sufficient to cover a significant fraction of the area under the plasma concentration versus time curve.

Serial blood samples for intensive PK monitoring will be collected on C1D1 and C1D8 for a total of 12 patients, blood samples for PopPK will be collected for all enrolled patients. PK parameters calculated from the drug concentrations in these samples will be used to compare the area under the concentration versus time curve from time 0 to infinity ($AUC_{0-\infty}$) on D1 with the area under the concentration versus time curve calculated during the dosing interval at steady state (AUC_{τ}) and detect any auto-inhibition or auto-induction of the pharmacokinetics of selpercatinib (none is expected). Exploratory analyses to determine the presence and structures of metabolites of selpercatinib may also be conducted and the results of these analyses, if conducted, will be reported separately by the Sponsor.

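### Protocol 9.4.4 takes AUC0-inf and its dependents from C1D8, a steady-state day, lists neither Day 1 nor AUCtau, and so conflicts with the synopsis and Section 7.7.3

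*Protocol*

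**What the plan says.** Three parts of the protocol describe the derivation of PK parameters, and they differ.

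- **Section 9.4.4:** "The following PK parameters will be calculated from plasma concentrations determined on C1D8". The list is Cmax, Tmax, AUC0-t, AUC0-inf, "apparent oral clearance (CL/F), apparent volume of distribution" and half-life. Day 1 and AUCtau are absent, and no formula for CL/F is given.
- **Synopsis, Pharmacokinetic Analyses:** "The following PK parameters will be calculated from plasma concentrations determined on Cycle 1 Day 1 and Day 8", followed by the same list.
- **Section 7.7.3:** AUC0-inf on Day 1 is to be compared with AUCtau at steady state, to detect a change in clearance with repeated dosing. On the window it says "The 0-8-hour duration of sample collection will be sufficient to cover a significant fraction" of the AUC, with no figure.

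Section 7.2, Table 7-1 and Section 8.4 set the sampling for the 12 intensive-PK patients. On C1D1 it is pre-dose and 1, 2, 4, 8 and 12 h. On C1D8 it is "pre-dose, and post-dose at 1, 2 and 4 hours", then 8 h, and nothing later.

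Section 9.1.2 makes PK a secondary endpoint: "Plasma concentrations of selpercatinib and PK parameters, including, but not limited to" AUC0-24, Cmax and Tmax. AUC0-24 is not in the list in 9.4.4. Section 9.4.3 leaves the analysis of other secondary endpoints to the SAP. The SAP repeats the PK objective in Section 4.2, but its Section 6 contains no PK analysis and Section 6.1.1 defines no PK population.

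**The concern.** By C1D8 a patient has been dosed twice daily for seven days. The curve after the morning dose includes drug still present from earlier doses. Extending it to infinity counts that residual drug as though the one dose had produced it, so AUC0-inf from this day is not the exposure from a single dose. At steady state the exposure from one dose is AUCtau, and apparent clearance is Dose/AUCtau. Section 9.4.4 lists the first quantity and omits the second.

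The 8 h stop is a separate difficulty. It does not cause the accumulation error, but it means that the terminal slope, and anything extrapolated with it, rests on a short window.

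PK characterization is a stated secondary objective, and Section 1.2 gives it as part of the reason for studying Chinese patients. An exposure roughly doubled by the method could be misread as a population difference or as inhibition of the drug's own clearance.

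**Working it through.** The plan gives no AUC ratio or clearance figure to reproduce, so this is a calculation from its own inputs.

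**Inputs**

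- Dosing interval tau: about 12 h (Section 6.2.1).
- Half-life: Section 6.3.2 equates "approximately 5 half-lives (approximately 2 to 3 days". Then 48/5 = 9.6 h and 72/5 = 14.4 h. This is the only half-life information in the documents, and it is approximate.
- Time from first dose to C1D8: 168 h, which is 168/14.4 = 11.7 to 168/9.6 = 17.5 half-lives. C1D8 is at steady state.
- Clearance constant over time: Section 7.7.3 expects no change.
- One compartment, bolus-like input to begin with. The absorption rate ka is not in the documents.

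**Accumulation alone.** With k = ln2 / half-life, superposing earlier doses gives

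R = AUC0-inf (from a steady-state dose) / AUCtau = 1 / (1 − exp(−k·12)).

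If CL/F were Dose/AUC0-inf, it would be too low by the fraction 1 − 1/R = exp(−k·12).

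| Half-life | exp(−k·12) | R | CL/F shortfall |
|---|---|---|---|
| 9.6 h | 0.420 | 1/0.580 = 1.73 | 42% |
| 14.4 h | 0.561 | 1/0.439 = 2.28 | 56% |

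**With assumed absorption.** At ka = 0.5 per h, R becomes 1.85 (9.6 h) and 2.42 (14.4 h), with shortfalls of 46% and 59%. These need a value that the documents do not supply.

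**Adding the real sampling times.** I simulated a non-compartmental analysis with samples at 0, 1, 2, 4 and 8 h and the terminal slope fitted on 2–8 h or 4–8 h. The ratio was 1.7 to 2.8 for bolus input and for ka of 1 or 2 per h. At ka = 0.5 per h it was 2.3 to 3.3 (half-life 9.6 h) and 3.2 to 4.9 (14.4 h). In the bolus case the part extrapolated beyond 8 h is exp(−k·8), or 56% and 68%.

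**Day 1.** AUC0-inf from C1D1 has no accumulation error. The part beyond 12 h is exp(−k·12), or 42% and 56% (bolus).

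**Check of the remedy.** AUCtau on C1D8 over 0–12 h, with the pre-dose value used as the 12 h concentration, came to 0.99 to 1.00 of the true value for ka from 0.3 to 2 per h.

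**The case against.** Several points on the other side stand.

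- **The clearance formula is not written.** A reader might infer that the plan commits to a CL/F about half its true value. It does not. Section 7.7.3 names AUCtau as the steady-state exposure. An analyst who divided the dose by it would have an error of about 1% or less. The shortfall is conditional.
- **The 8 h stop is not the source of the 1.7 to 2.3.** That factor is accumulation and would be the same with sampling to 48 h. The short window is a further error on top of it.
- **The half-life is soft.** It comes from an approximate recommendation about holding treatment, not from a PK estimate. Anything above 2.3-fold or 56% needs further assumptions about absorption or about how the terminal slope is fitted.
- **The check for auto-inhibition or auto-induction is not broken.** A reader might infer this from the list in 9.4.4. But Section 7.7.3 specifies that comparison itself, and its Day 1 and Day 8 samples are collected. The fault is an inconsistent list.
- **AUC0-24 is not out of reach.** Neither day is sampled to 24 h, but at steady state AUC0-24 is twice AUCtau.
- **The consequence is limited.** These are descriptive summaries in 12 patients, and the documents rest no test and no ORR analysis on them.

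None of this removes the conflict between the three protocol sections, or the fact that the operative list pairs AUC0-inf with a steady-state day.

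**Conclusion.** The point holds as a matter of wording with a numerical consequence. Section 9.4.4, read literally, would report an AUC0-inf from C1D8 about 1.7 to 2.3 times the dose-interval exposure through accumulation alone. CL/F would be about 42 to 56% too low only if it were computed as Dose/AUC0-inf. Both ranges rest on a half-life of 9.6 to 14.4 h, a 12 h interval, linear one-compartment kinetics and bolus-like input. Slower absorption, or a terminal slope taken from samples ending at 8 h, would push the error up.

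Vz/F is affected both by accumulation and by the short window. Half-life is affected only by the window, which on C1D8 is shorter than one half-life across the assumed range. On C1D1 the 12 h window exceeds the lower end of that range. The change should be made before the PK analysis, but the issue does not touch the primary endpoint.

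**What to change.** Reconcile the synopsis, Section 7.7.3 and Section 9.4.4 by stating the parameters for each day.

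- **C1D1:** Cmax, Tmax, AUC0-12, and AUC0-inf reported together with its extrapolated fraction.
- **C1D8:** Cmax, Tmax, AUCtau over 0–12 h with the pre-dose value as the 12 h concentration, CL/F = Dose/AUCtau, and AUC0-24 = 2 × AUCtau. Drop AUC0-inf from this day. Report half-life and Vz/F only with a caveat about the short sampling window.

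Using the pre-dose value assumes that the dosing interval was close to 12 h. Section 6.2.1 allows as little as 6 h between doses, so the recorded times of the preceding doses (Section 8.4) should be checked for each patient.

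Moving half-life and Vz/F to a population PK model is not a ready answer: the PopPK samples are pre-dose only (Table 7-1, Section 7.3) and no model is described.

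The cost is protocol and PK-plan wording. No new samples are needed.
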